## **Abstract**

Respiratory and phonatory systems undergo various changes with age that can lead to changes in voice production. This condition is known as Presbyphonia. As respiratory muscles play a pivotal role in voice production. We aim to use an expiratory muscle strengthening training (EMST) device, in addition to standard therapy (Phonation resistant training exercise - PhoRTE) to improve voice outcomes in patients with Presbyphonia. The subjects with vocal atrophy will be enrolled and randomized into two groups: (a) Only Phonation resistant training exercise (PhoRTE) (b) PhoRTE with EMST. The outcomes measures will be pre and post acoustic and aerodynamic measures, Voice Handicap Index - 10 (VHI – 10), and Aging Voice Index (AVI).

## **Background and Introduction**

The phonatory and respiratory systems undergo many age-related changes in their anatomy and physiology that can lead to undesirable effects on the voice. These changes have detrimental effects on the lives of elderly individuals. Few studies have evaluated the use of voice therapy treatment options for age-related voice disorders. The aim of this study is to compare a voice therapy program developed specifically for patients diagnosed with presbyphonia, Phonation Resistant Training Exercises (PhoRTE), with and without the addition of an expiratory muscle strength training (EMST) protocol that has been shown to strengthen the expiratory respiratory muscles. We hypothesize that the addition of EMST to PhoRTE is at least as effective as PhoRTE alone in treating vocal fold atrophy in elderly patients.

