## **Objective**

The primary objective of this study is to identify if there is additional benefit of providing EMST training to the individuals with Presbyphonia. We aim to compare the outcome measures between the two groups to conclude the results.

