### *VHI-10*

The primary outcome is the Voice Handicap Index-10 (VHI-10) score. The VHI-10 is a patient-centered outcome that quantifies a patient's perception of handicap caused by a voice disorder and will be measured at every session. VHI-10 will be anchored to baseline VHI-10 score (each item anchored) for the 1 week follow-up (will be administered without anchoring). Secondary outcomes include the following:

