### *Participants*

N=28 male and female participants diagnosed with vocal fold atrophy. 14 patients will be recruited for each arm of the study.

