## Safety

### *Adverse Events*

An interim analysis will be conducted at the midpoint of the study to ensure that PhoRTE+EMST is safe. During the study, each participant will be asked if they perceive their treatment to be harmful to them. If participants evince a VHI-10 increase of greater than 5 points *in addition to* reporting that voice therapy is harmful, then the study will be paused, re-evaluated, and possibly terminated. The study statistician ([name]) will perform this interim analysis: clinical investigators will remain blinded to the results in order to avoid bias. Clinical investigators will only be informed of results if there is a substantial safety concern by the midpoint of the study.

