## Data Analysis Plan

The purpose of the study is to measure any differences in the two study arms. Thus, t-test will be performed. Descriptive statistics will be utilized to identify the normality of the data.

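### The only stated hypothesis is a non-inferiority claim with no margin, but the objective and the one planned between-arm test concern a difference, so a non-significant result cannot support it

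*Combined protocol and SAP*

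**What the plan says.** The protocol states its aim in four places.

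- **Abstract:** EMST is added to standard therapy "to improve voice outcomes in patients with Presbyphonia".
- **Background and Introduction:** the sole hypothesis is that "the addition of EMST to PhoRTE is at least as effective as PhoRTE alone".
- **Objective:** the primary objective is to "identify if there is additional benefit of providing EMST training". The section continues: "We aim to compare the outcome measures between the two groups to conclude the results".
- **Data Analysis Plan:** "The purpose of the study is to measure any differences in the two study arms. Thus, t-test will be performed".

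The measure is fixed in the VHI-10 section: "The primary outcome is the Voice Handicap Index-10 (VHI-10) score". The size is fixed under Participants: "14 patients will be recruited for each arm of the study". The documents give no non-inferiority margin, confidence-interval rule, alpha, sidedness, SD or power calculation. The only VHI-10 threshold is in the Adverse Events section ("If participants evince a VHI-10 increase of greater than 5 points"), where it forms part of a safety pause rule.

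**The concern.** The Abstract, the Objective and the Data Analysis Plan fit together: they look for a benefit, or at least a difference, and test for one. The hypothesis is the outlier. It would be true if EMST added nothing and did no harm, and a test of equality is not built to show that. Failing to reject equality is not evidence that the combination is no worse.

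As written, the trial has two possible routes to a favourable conclusion: added benefit if the test is significant, and confirmation of the stated hypothesis if it is not. The plan does not say that a null result will be read in the second way, but nothing in it rules that out. The Summary expects the results to help clinicians improve outcomes. A null result from 28 patients, presented as confirming the hypothesis, could leave a real disadvantage of the combination undetected.

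**Working it through.** **Inputs.** From the documents: VHI-10 as primary outcome, two arms, 14 per arm, a t-test between arms. A rise in VHI-10 is a worsening (Adverse Events section). Assumed, because the documents are silent: two-sided alpha 0.05, a two-sample test with 26 degrees of freedom, all 28 analysed, and a VHI-10 SD of 5, 7 or 10 points. The SD of change scores could differ.

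**The plan's own figure.** 14 + 14 = 28 agrees with the stated total. Nothing more can be reproduced, since no effect size, SD, alpha, power or margin is given.

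**Step 1: the arms are truly equal.** The hypothesis is then true. A two-sided 0.05 test gives significant benefit in 2.5% of trials (supports the hypothesis), no significance in 95% (settles nothing) and significant worsening in 2.5% (wrongly contradicts it). This needs no SD.

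**Step 2: what an observed difference of zero leaves open.**

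- SE = SD × √(2/14) = 0.378 SD
- t(0.975, 26 df) = 2.0555
- 95% half-width = 2.0555 × 0.378 SD = 0.777 SD
- At SD 5, 7 and 10: 3.88, 5.44 and 7.77 points

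So even an estimate of exactly zero is compatible with the combination being about 4 to 8 points worse over this range of SDs.

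**Step 3: how often a true worsening is non-significant.** Noncentral t with noncentrality (worsening/SD) × √(14/2). The 5 and 3 points are illustrations, not margins.

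| True worsening | SD | Significantly worse | Non-significant, estimate favours PhoRTE alone | Non-significant, estimate zero or better |
|---|---|---|---|---|
| 5 points | 5 | 72.1% | 27.5% | 0.4% |
| 5 points | 7 | 44.4% | 52.6% | 2.9% |
| 5 points | 10 | 24.7% | 66.1% | 9.2% |
| 3 points | 5 | 33.3% | 61.1% | 5.6% |
| 3 points | 7 | 19.3% | 67.9% | 12.7% |
| 3 points | 10 | 11.6% | 67.0% | 21.1% |

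Rows fall slightly short of 100% where there is a small chance of significance in the wrong direction, and through rounding. In total, a true 5-point worsening is non-significant in 28%, 56% or 75% of trials, and a 3-point worsening in 67%, 81% or 88%.

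**Step 4: what 14 per arm could deliver as a non-inferiority trial.** With one-sided 0.025, 80% power and no true difference, the margin would have to be 1.10 SD, which is 5.5, 7.7 or 11.0 points at SD 5, 7 or 10. An illustrative margin of 0.5 SD would need 64 per arm.

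**The case against.** The strongest reply is that the operative plan is already coherent. Objective and analysis agree, the t-test suits the objective, and the mismatch is one sentence in a background section that no decision rule relies on. The plan never says a null result will be read as confirmation, and any difference test is usually non-significant when there is no effect. The Summary also hopes the study will lead to further ones, which is a modest ambition. On size, the point figures rest on assumed SDs. The most deceptive outcome, a non-significant result with an estimate of zero or better despite a true worsening, is the least common non-significant outcome: 0.4% to 9% for 5 points and 6% to 21% for 3 points. Finally, rewording the hypothesis as superiority makes it directional, whereas the Data Analysis Plan is not.

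Much of this is fair and limits the weight of the point. The t-test is not wrong for the stated objective, and in most misleading cases the estimate would visibly favour PhoRTE alone. But that sentence is the only hypothesis in the protocol, and the documents nowhere call the study a pilot. The logical gap does not depend on any SD. If the wording was simply loose, the correction states what was meant. A directional hypothesis can be examined with a two-sided test, so the reworded sentence does not conflict with the planned analysis.

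**Conclusion.** The point holds. Followed as written, the plan can support its own hypothesis only if the combination is significantly better. If the arms are equal, so that the hypothesis is true, that happens in 2.5% of trials, and 95% end without an answer. This rests on a two-sided 0.05 between-arm t-test, which the documents do not specify in full.

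The sizes in points are conditional on SDs of 5 to 10 and complete data; dropout would widen the interval. The mismatch does not invalidate the test of added benefit. It leaves the stated hypothesis without a valid decision rule, and should be corrected before the data are analysed.

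**What to change.** Bring the hypothesis into line with the Abstract, the Objective and the Data Analysis Plan.

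1. In Background and Introduction, replace the hypothesis with: *The hypothesis is that adding EMST to PhoRTE gives a better VHI-10 outcome than PhoRTE alone.*
2. In the Data Analysis Plan, add: *The between-arm difference in VHI-10 will be reported with its 95% confidence interval. A non-significant t-test will not be reported as evidence that PhoRTE+EMST is no worse than PhoRTE alone.*

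This costs three sentences and no patients or data. The price to the sponsor is that a null result can no longer be presented as confirming the hypothesis.

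If the sponsor prefers to keep the non-inferiority wording, it must prespecify and justify a between-arm VHI-10 margin, conclude only if the confidence limit on the worse side excludes that margin, and state what 28 patients deliver against it. Step 4 suggests this may require more patients. The 5-point trigger in the Adverse Events section should not be borrowed as the margin: it describes an individual's own change and counts only together with that person's report of harm.

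The t-test's time point, score (final or change), sidedness and alpha are also unstated. That is a separate gap, which must be closed before the reported difference is fully defined.

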## **Objective**

The primary objective of this study is to identify if there is additional benefit of providing EMST training to the individuals with Presbyphonia. We aim to compare the outcome measures between the two groups to conclude the results.

## **Outcomes**

Outcomes will be collected at the start of the study, at the start of each therapy session, and during one-week post-therapy follow-up.

This study is a two arm, prospective randomized investigation to examine the impact of PhoRTE and EMST on VHI-10, AVI, acoustic, aerodynamic, and auditory-perceptual outcomes collected pre-(baseline) and post-intervention (short-term follow-up).

### *VHI-10*

The primary outcome is the Voice Handicap Index-10 (VHI-10) score. The VHI-10 is a patient-centered outcome that quantifies a patient's perception of handicap caused by a voice disorder and will be measured at every session. VHI-10 will be anchored to baseline VHI-10 score (each item anchored) for the 1 week follow-up (will be administered without anchoring). Secondary outcomes include the following:

### *AVI*

The Aging Voice Index (AVI) is a new patient-centered outcome that quantifies quality of life impact a voice disorder has on older adults. It will be compared at baseline and during the final 1-week follow up.

### *Aerodynamic Measures*

Average airflow in speech, average number of breaths, average duration of a standard reading passage (The Rainbow Passage). Our prior work has demonstrated sensitivity to change following treatment for these acoustic and aerodynamic measures.

### *Acoustic Measures*

Cepstral Spectral Index of Dysphonia (CSID), a multifactorial estimate of dysphonia severity that correlates with the visual analog scale for overall voice severity used in the Consensus Auditory-Perceptual Evaluation of Voice (CAPE-V), Cepstral Peak Prominence and its standard deviation, Cepstral Peak Prominence Fundamental Frequency (CPP F0) and its standard deviation, and average vocal intensity in dB SPL.

### *Voice Quality by Blinded Raters*

Overall voice severity determined by CAPE-V score provided by blinded raters.

## **Study design and Methods**

This is a prospective study. University of Pittsburgh will be recruiting patients as well under their own IRB. Emory participants will be voice patients from the Emory University Voice Center. A research coordinator will review clinic schedules to identify potential participants and will alert the clinical team members by affixing a notice to the potential participant's chart. Once the clinical team has determined eligibility for the study based on evaluation/diagnosis, potential participants will be contacted and offered the opportunity to participate in the study. If the patient agree to participate they will be randomized to either of the study arms: (a) Only PhoRTE (b) PhoRTE with EMST. A randomization table will be created prior to recruit to determine the treatment assignment for each patient.

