**Intervention/Experimental Protocol**

*Outline Of Procedures*

The experimental protocol consists of pre-treatment and post-treatment acoustic and aerodynamic data collection and four 45-minute sessions of voice therapy. All subjects will complete PhoRTE therapy, and those in the EMST+PhoRTE arm in the study will also undergo EMST training. Before each PhoRTE therapy, subjects will report to the PI so that therapists are blinded as to which treatment group each subject is in.

Baseline	Therapy 1	Therapy 2	Therapy 3	Therapy 4	Post-Tx
Pre-Tx Acoustic and Aerodynamic Measurements, VHI-10, AVI, MEP	PhoRTE +/- EMST  VHI-10 MEP	PhoRTE +/- EMST  VHI-10 MEP	PhoRTE +/- EMST  VHI-10 MEP	PhoRTE +/- EMST  VHI-10 MEP	Acoustic and Aerodynamic Measurements, VHI-10, AVI, MEP

*PhoRTE Therapy (Standard of Care Treatment)*

Each therapy session will last for 45 minutes.

1st PhoRTE treatment session

- Check in with your patient about current status
  - o Do you have any questions since we last met? Do you have any concerns about your ability to commit to PhoRTE?
- Check in with the patient to verify implementation of voice care program
  - o Dehydration, non-phonatory inflammation (reflux, illness)
  - o Phonotrauma (throat clearing, cough)
  - o Caffeine
- Provide patients with PhoRTE therapy information sheets, phrase list, and practice sheets
- Set up the patient for home practice
  - o Verify that patient is able to download a decibel meter app successfully, and configure the app’s settings with a sound pressure level meter for home practice

- Orient the patient to the app; teach them how to open and utilize the app for home practice; demonstrate for the patient how to standardize mic-to-mouth distance
- Verify that 10 functional phrases for practice are written. Review phrases for length and that they are representative of typical communication
- Teaching proper breathing form
  - Establish efficient respiratory mechanisms to effectively execute PhoRTE exercises
  - Ex. "Place your hand on your upper abdomen just above your belly button. Now, I want you to sustain the sound "sh" for as long as is comfortable. Notice the inward movement of your hand as you exhale and sustain "sh." Let's practice this breathing a few more times until you feel comfortable with this task."

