### Data collection and Management

Research Electronic Data Capture (REDCap), will be used to manage all participant data from initial screening through study completion. Each subject will be given a subject number and patient's identifying information will be stored in the database. Once the data collection is completed, the data will be downloaded from the REDcap application in a way that all personal health identifiers are removed. The deidentified data will be stored in a secure Emory server and shared with University of Pittsburgh for the purpose of analysis. All the personal identifiers will be kept only in REDcap database until the completion of study.

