### *Auditory Perceptual Analysis*

3 blinded raters (tbd) will listen to the sentence “we were away a year ago” and rate on 100mm VAS in REDCap. The initial and final evaluations will be rated, for a total of 2 samples per participant x 28 participants = 56 samples.

Raters will be paid \$20/hour for ratings. Ratings should take in total 2 hour-long sessions.

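### Two sites recruit, but the plan does not specify stratification by site and its only between-arm analysis is a t-test with no site term, which costs precision if the sites differ

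*Combined protocol and SAP*

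**What the plan says.** Study design and Methods names the Emory University Voice Center as the source of Emory participants and adds that "University of Pittsburgh will be recruiting patients as well under their own IRB". On allocation it says "A randomization table will be created prior to recruit to determine the treatment assignment for each patient". Stratification, blocking, the number of tables and concealment are not mentioned there or elsewhere.

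Participants gives "N=28 male and female participants diagnosed with vocal fold atrophy" and "14 patients will be recruited for each arm of the study", with no split by site. Two other places bear on whether 28 is the whole trial. Auditory Perceptual Analysis counts "2 samples per participant x 28 participants = 56 samples", and Data collection and Management says that de-identified data will be "shared with University of Pittsburgh for the purpose of analysis".

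The Data Analysis Plan names one comparative method: "Thus, t-test will be performed". The only addition is descriptive statistics to look at normality. No site term or covariate is named.

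**The concern.** In a two-site trial of 28, an allocation list that ignores site can leave one site over-represented in one arm. An unadjusted comparison then carries part of any site difference into the estimated EMST effect. Any real site difference in VHI-10 also stays in the error term.

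A site difference is plausible. Eligibility requires only VHI-10 ≥1, so the two clinics could enrol patients of quite different severity. The documents give no estimate of its size.

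The analysis side is more than a missing detail, because the t-test is a stated method. As shown below, it is no better than a site-adjusted model on site-stratified lists in any case examined, and it is worse when the sites differ, however the table is built.

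**Working it through.** **Inputs from the documents.** Two recruiting sites; N = 28; 14 per arm; t-test; primary outcome VHI-10.

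**Assumptions, because the documents are silent.** The 28 are pooled over both sites. The smaller site has n = 8, 10 or 14 patients. The site difference s is 0, 0.5 or 1.0 within-site SD. Alpha is two-sided 0.05 and there is no dropout. The plan gives no power calculation, so there is no figure of its own to reproduce. For scale, 14 per arm gives 80% power for a difference of about 1.10 SD (noncentral t), so 1.1 SD is used as the true effect.

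**Step 1: chance of imbalance with one unstratified 14/14 list.** The number X of a site's n patients who fall in one arm is hypergeometric: P(X = x) = C(14,x)·C(14,n−x)/C(28,n).

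- n = 14, split 9:5 or worse: 2·(2002² + 1001² + 364² + 91² + 14² + 1²)/40,116,600 = 10,301,958/40,116,600 = 0.257.
- n = 8, split 6:2 or worse: 2·(273,273 + 48,048 + 3,003)/3,108,105 = 648,648/3,108,105 = 0.209.
- n = 10, a gap of 4 or more: 0.236.

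**Step 2: effect of such a split on the estimate.** A gap of 4 patients changes the site mix between arms by 4/14 = 0.286. The arm difference moves by 0.286 × s, which is 0.14 SD at s = 0.5 and 0.29 SD at s = 1.0.

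**Step 3: average precision.** Over all unstratified 14/14 allocations, SE = √[(2/14)·(1 + s²·n(28−n)/(28·27))].

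- s = 0: √(2/14) = 0.378 SD.
- s = 1.0, n = 14: √(0.1429 × 1.259) = 0.424 SD.
- s = 1.0, n = 10: √(0.1429 × 1.238) = 0.421 SD.

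**Step 4: power for a true effect of 1.1 SD.** Simulation, 100,000 runs per cell, n = 8, 10 and 14:

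| Site difference | Unstratified, t-test | Unstratified, site term | Stratified, t-test | Stratified, site term |
|---|---|---|---|---|
| 0 | 0.80 | 0.78 | 0.80 | 0.80 |
| 0.5 SD | 0.78 | 0.78 | 0.78 | 0.80 |
| 1.0 SD | 0.70–0.72 | 0.78 | 0.72–0.74 | 0.80 |

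Type I error is about 0.05 for the unstratified t-test and for both site-adjusted analyses. For the t-test on stratified lists it falls to about 0.04 at s = 0.5 and about 0.03 at s = 1.0. That test counts the site variation as error, although the design has already removed it from the arm comparison.

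**The case against.** The strongest reply is that the documents do not say the table is unstratified. They are silent, and since Pittsburgh works under its own IRB it may hold its own list. That stands, and it limits the allocation point to a request to specify. It does not rescue the analysis: with stratified lists the plain t-test is conservative and gives up most of the gain.

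Second, 28 might be Emory's number alone. That cannot be excluded. The count of 56 rated samples and the sharing of data for analysis favour a pooled 28 without proving it. If 28 is Emory only, the site-split figures above do not apply to it.

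Third, the benefit depends on a site difference that nobody has quantified. This also stands: at 0.5 SD the gain is about 2 percentage points of power, and at zero there is none.

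Three stronger readings are tempting but unsupported:

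- A reader might infer that the t-test is biased or has inflated type I error. It does not: randomisation makes it unbiased on average, and the simulated error rate stays near 0.05.
- A reader might infer that each site has its own therapists, equipment and EMST coach, and that site strata would balance them. The protocol says only that "subjects will report to the PI so that therapists are blinded as to which treatment group each subject is in", without giving the therapists' number or site. Strata by site would not balance therapists within a site.
- A reader might infer that 14 per arm cannot be secured as planned. A 28-row table with 14 of each would deliver it.

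**Conclusion.** The point holds as one of precision and chance imbalance, not of validity. Two sites recruit, stratification by site is not specified, and the stated analysis ignores site. On one unstratified list there is roughly a one-in-five to one-in-four chance of a gap of 4 or more patients at a site, and the estimate in this one trial then moves by at least 0.29 of the site difference.

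At a 1 SD site difference, the combination of stratified lists and a site term recovers 8 to 10 percentage points of power. With 80% power only for effects of about 1.10 SD, the trial has little precision to spare. These sizes rest on a pooled 28, the assumed site splits and site differences, two-sided alpha 0.05 and no dropout. The change is worth making before recruitment because it costs so little.

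**What to change.** 1. State in Participants whether 28 covers both sites, and give the planned split.
2. In Study design and Methods, replace the single sentence on the table with one permuted-block list per site, with the next assignment concealed from those who enrol.
3. In the Data Analysis Plan, replace the t-test on VHI-10 with a linear model with arm and site as fixed effects. Baseline VHI-10 is already collected and can be added.

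Make changes 2 and 3 together. Stratifying while keeping the t-test makes the test conservative. Adding the site term to an unstratified list loses about 2 points of power if the sites turn out alike.

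The cost is one degree of freedom for site (25 rather than 26 residual), two lists instead of one, and a possible departure of a patient or so from exactly 14/14 if a block is left incomplete. No extra patients are needed.
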